Resolving Psychological Stress

**University of San Francisco, California
San Francisco Veteran's Affairs Health Care System**

Principal Investigator: [name]

NCT03996876

Document Date: 9/11/2020

Study Protocol

Overview:

We will perform a phone screen or have participants fill out an online eligibility survey to determine eligibility for the study. Based on the answers to the screening questions, we will invite potentially eligible participants to attend an appointment at the San Francisco Veterans Affairs Medical Center to complete baseline assessments to include eligibility assessments and baseline testing. We may ask the questions from the eligibility screening in person if this is requested by the interested potential participant. The eligibility assessment will include the Clinician Administered PTSD Scale and the Structured Clinical Interview for the American Psychiatric Association's Diagnostic and Statistical Manual-V. For participants who are eligible after these assessments, we will complete baseline testing, which will include psychological and physiological tests. The eligibility and baseline assessments can take place over the course of one or two appointments. Following this, participants will be instructed on how to use the mobile app and how to complete the 15 days of training and assessments. Finally, after completing this program of training and assessments, they will return to the lab for follow-up assessments.

Inclusion Criteria:

To qualify for participation, participants will: 1) have current chronic PTSD (full- or sub-threshold) as defined by DSM-V criteria lasting at least 3 months and meeting at least one DSM-V criteria for threat sensitivity; 2) be aged 18-75; 3) have the ability to understand and comply with the training protocol and complete study assessments; 4) be either veterans or non-veterans; 5) have a DSM-V diagnosis of Alcohol Use Disorder.

Exclusion Criteria:

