The 15-day training and assessment phase will take place with the assistance of a mobile application called REPS (Resolving Psychological Stress). Eligible consenting participants will perform REPS training and assessments on the mobile application for 15 days. Participants will have up to three weeks to complete all the sessions. Participants will be instructed to complete a total of twelve days of training in conjunction with daily assessments of mood, stress, sleep and unusual events as well as three days of a more thorough assessment of mood, stress, depression, anxiety and PTSD symptoms once per week on the device. The training days involve approximately 15-minute long sessions of the REPS paradigm dot probe training and daily questions on the mobile app. Weekly assessment days should take 20 minutes on the mobile app. Participants may contact study personnel during office hours with questions or concerns via telephone or through email. We will contact participants by phone once per week to assess adherence to the protocol and to ensure that their device is functioning properly. We will assess adherence only by self-report. App-based follow-up assessments will take place at the end of 12 days of training. For participants who have not completed 12 days of training within 21 days of the start of training, we will push a follow-up assessment, which they will be asked to complete as soon as possible.

REPS Paradigm

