Each training session with daily questions will last for approximately 15 minutes. At the beginning of the session, participants will be asked to report on their mood and emotions and stress exposure before beginning the REPS training session. During the training session, they will be exposed to threatening words in the ABM condition (e.g., death, crazy, worry) or neutral words in the control condition (e.g. hill, jersey, check). These are chosen based on their own ratings of 50 words. The ratings are entered into an algorithm which determines the most threatening words for that participant. On each trial, the participants will be exposed to a threatening (ABM) or neutral (control) word and a matched neutral word for a very brief period of time (500ms). The words will then disappear and one of them will be replaced by a probe in the form of either the letter E or F and the participant will be asked to indicate whether an E or an F appears. In the ABM training paradigm, the probe will replace the neutral stimulus all of the time, which is thought to train the participants to direct their attention towards a neutral stimulus in the context of a threatening stimulus. In the control condition, the probe will replace one set of neutral stimuli all of the time. There will be a brief inter-trial break (e.g., 500 - 1500 ms) between each trial. The participant will complete this training task for last approximately 10 minutes with an additional 5 minutes of daily questions.

Statistical Analysis Plan

Power analysis: This study is designed to yield estimates of effect size rather than to complete a definitive trial of ABM in PTSD.

Statistical Analyses: Descriptive analyses of behavioral and questionnaire data are used to assess feasibility and acceptability of REPS. Exploratory analyses examine the effects of intervention (attention bias modification versus control training) x time (baseline, follow up) on PCL-5 (PTSD Checklist-5) scores using mixed models. The PCL-5 was given via the mobile application immediately before participants starting their threat-related attention bias or neutral control attention training and at follow-up.

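### The exploratory PCL-5 intervention-by-time model states no baseline adjustment; if allocation is random, its between-arm estimate is unbiased but usually less precise than an adjusted one

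*Combined protocol and SAP*

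**What the plan says.** The Statistical Analyses paragraph of the SAP describes the PCL-5 analysis in one sentence: the exploratory effects of "intervention (attention bias modification versus control training) x time (baseline, follow up) on PCL-5 (PTSD Checklist-5) scores using mixed models". Baseline PCL-5 therefore enters as one level of the outcome. The text mentions no baseline covariate, no constraint of the two arms to one baseline mean, no covariance structure and no missing-data assumption.

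Three other places bear on the point:

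- **Purpose** (SAP, Power analysis): "This study is designed to yield estimates of effect size rather than to complete a definitive trial of ABM in PTSD". No sample size, SD, alpha or power is given.
- **Timing of the baseline** (SAP, Statistical Analyses): "The PCL-5 was given via the mobile application immediately before participants starting their threat-related attention bias or neutral control attention training and at follow-up". The baseline score is thus taken before training and can properly be adjusted for.
- **Follow-up** (15-Day Training and Assessment Phase): "For participants who have not completed 12 days of training within 21 days of the start of training, we will push a follow-up assessment". Late completers are pursued, but some follow-up scores may still be missing.

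Two conditions are compared, "attention bias modification versus control training", but nowhere is it said that participants are allocated to them at random.

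**The concern.** An unconstrained group-by-time model with two time points estimates each arm's baseline mean separately, and its interaction compares the arms on change. If allocation is random, the true baseline means are equal and any observed baseline difference is chance. Subtracting baseline in full (a slope of 1) is generally not the best way to remove that chance difference. The best slope is the regression of follow-up on baseline.

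Precision is at stake, not bias. No decision hangs on this exploratory analysis, so its importance is limited. It is nevertheless the only between-arm comparison the SAP specifies, in a study whose stated product is effect-size estimates, and the choice affects the width of that estimate's interval.

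**Working it through.** **Inputs.** The plan has no figure to reproduce. Assumed here: random 1:1 allocation; baseline SD 1; follow-up to baseline SD ratio k; baseline to follow-up correlation rho; total sample N; fraction m without follow-up, missing completely at random and equally in both arms.

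**Step 1: what the planned contrast is.** In a mixed model fitted to one simulated complete data set, the group-by-time interaction was 0.42269 and the difference in mean change was 0.42269.

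**Step 2: large-sample variances per person, complete data.**
- Change: 1 + k² − 2·rho·k
- Adjusted: k²(1 − rho²)
- Difference: (1 − rho·k)², which is never negative

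Allowing for missing follow-up, let A = k²(1 − rho²)/(1 − m). The ratio adjusted/planned is A / (A + (rho·k − 1)²).

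Example, k = 1, m = 0, rho = 0.5: A = 0.75 and (0.5 − 1)² = 0.25, so the ratio is 0.75/1.00 = 0.75. For k = 1 and m = 0 the formula reduces to (1 + rho)/2.
Example, k = 1, m = 0.25, rho = 0.5: A = 0.75/0.75 = 1.00, so the ratio is 1.00/1.25 = 0.80.

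**Step 3: small-sample cost.** With complete data, estimating the slope multiplies the adjusted variance by (N − 3)/(N − 4): 37/36 = 1.028 at N = 40 and 17/16 = 1.0625 at N = 20.

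| Setting | rho 0.5 | rho 0.7 | rho 0.9 |
|---|---|---|---|
| k = 1, large sample, complete | 0.750 | 0.850 | 0.950 |
| k = 1, large sample, 25% missing | 0.800 | 0.883 | 0.962 |
| k = 0.8, large sample, complete | 0.571 | 0.628 | 0.608 |
| k = 1.2, large sample, complete | 0.871 | 0.966 | 0.977 |
| k = 1, N = 40, complete | 0.771 | 0.874 | 0.976 |
| k = 0.8, N = 40, complete | 0.587 | 0.645 | 0.625 |
| k = 1.2, N = 40, complete | 0.895 | 0.993 | 1.004 |
| k = 1, N = 20, complete | 0.797 | 0.903 | 1.009 |
| k = 1.2, N = 20, complete | 0.925 | 1.027 | 1.038 |

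Interval width follows the square root of the ratio. In the first row, √0.75 = 0.866, √0.85 = 0.922 and √0.95 = 0.975, so intervals are 13%, 8% and 2.5% narrower. In the second row they are 11%, 6% and 2% narrower. Equivalently, in the first row the change contrast needs 1/0.75, 1/0.85 and 1/0.95 times as many participants: about 33%, 18% and 5% more.

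**Step 4: where the gain disappears.** At k = 1, setting (1 + rho)/2 × (N − 3)/(N − 4) = 1 gives break-even at rho = 0.882 for N = 20 and 0.946 for N = 40. For other k, the gain vanishes when rho·k is near 1. There the ratio is the factor in Step 3, so the largest loss is about 3% of variance at N = 40 and 6% at N = 20. Eligibility requires participants to "have current chronic PTSD (full- or sub-threshold) as defined by DSM-V criteria lasting at least 3 months". That may narrow the baseline spread, so k above 1 is possible.

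**Step 5: simulation.** With 15 or 30 per arm, k = 1 and a true effect of −0.5 SD, both contrasts averaged between −0.498 and −0.503. The ratios at rho 0.5, 0.7 and 0.9 were 0.778, 0.879 and 0.984 (15 per arm) and 0.769, 0.871 and 0.963 (30 per arm). With 30 of 40 followed up, they were 0.818, 0.909 and 0.989 at k = 1, and 0.927, 1.001 and 1.010 at k = 1.2, with no bias.

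**Step 6: the two adjusted forms agree.** With two time points, a common baseline mean and an unstructured covariance, the likelihood splits into a baseline part and the regression of follow-up on arm and baseline, with separate parameters. The arm contrast is therefore the regression estimate, and participants without follow-up add nothing to it. In nine simulated data sets the two matched to five decimals (0.38881 in the first). Under compound symmetry the first gave 0.35048 instead.

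**Step 7: interval coverage.** The regression t interval covered 0.949 to 0.951. A plain Wald interval from the constrained REML model covered 0.935 to 0.936 (N = 40, complete), 0.930 (30 of 40 followed up) and 0.916 to 0.919 (N = 20, complete).

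**The case against.** The planned model is conventional, valid and labelled exploratory, so on one view this is a preference between two sound estimators. A one-sentence description does not rule out a common-baseline model. Random allocation, on which the comparison depends, is not stated. Correlation, SDs, sample size and dropout are all assumed, and the ratios run from a clear gain to a small loss. A follow-up only about two to three weeks after baseline makes a high correlation plausible, which at equal SDs points to the small end of the gain. At N = 20 with k = 1.2, adjustment already loses slightly at rho 0.7 (1.027). Finally, the SAP describes PCL-5 collection in the past tense, so a change now might come after the data were seen.

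Much of this stands as a limit on the point's weight. The gain is unknown and could be nil or slightly negative, and the accurate description is that adjustment is not stated, not that it is excluded. It does not remove the point. The recommendation depends on random allocation, the possible loss is a few percent of variance against gains that can reach about 40% (0.587 at N = 40, k = 0.8, rho 0.5), and naming the estimator settles an ambiguity whichever contrast is chosen. If the choice follows sight of the data, that can be reported.

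**Conclusion.** The concern holds, at low importance. As written, the model states no baseline adjustment, and its ordinary contrast is the difference in mean change. Given random allocation, and follow-up that is complete or missing at random, that contrast is unbiased. It is usually less precise than the adjusted one: with equal SDs, the adjusted variance is roughly 0.75 to 0.95 of the planned variance for correlations of 0.5 to 0.9 in large samples. The SD ratio matters as much as the correlation. Little or nothing is gained at very high correlation with about 20 participants, or when the correlation times the SD ratio is near 1. All of these sizes rest on assumed inputs. If allocation is not random, neither the unbiasedness nor the precision comparison can be taken for granted.

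**What to change.** State in the SAP whether allocation is random.

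**If it is random**, make the between-arm PCL-5 estimate baseline-adjusted and report it with its 95% CI, in one of two ways:
- regress follow-up PCL-5 on arm and baseline PCL-5; or
- keep the mixed model, constrain both arms to one baseline mean, and name an unstructured covariance and a small-sample interval method.

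The two give the same arm contrast, so retention of participants without follow-up is no reason to prefer either.

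**If it is not random**, do not impose a common baseline mean. State whether the change contrast or the adjusted contrast is intended.

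If PCL-5 data had been seen when the estimator was chosen, say so. The cost is one or two sentences of SAP wording and no new data, plus one degree of freedom for the slope and the possible few-percent loss of precision described above.
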